### Objectives, Endpoints, and Estimands

Objectives	Estimands	Endpoints
Primary:	Primary:	Primary:

 
Evaluate the long-term safety and tolerability of recifercept doses and dosing regimes in participants aged <math>\geq 15</math> m to <math>< 12</math> years with achondroplasia.
 
	N/A.	Long-term Safety and tolerability of recifercept as assessed through frequency and severity of AEs/SAEs.

 
To assess long-term efficacy of recifercept to increase height growth in children with achondroplasia.
 
	
 
The primary efficacy estimand is intended to provide a population level estimate of the effect of the IP on a continuous endpoint.
 
 
Population-level summary: ratio between participants in the trial and a reference population [Merker et al, 2018] in growth of height at 24 month; ratio between treated and reference population is observed change-from-baseline of treated participants standardized by reference participant given age and gender.
	
 
Increase in height growth above expected in reference population [Merker et al, 2018].
 

Secondary:	Secondary:	Secondary:

 
To evaluate the PK of recifercept in children aged <math>\geq 15</math>m to <math>\leq 12</math> years old with achondroplasia.
 
		Population PK characterization in children aged $\geq 15$ m to $< 12$ years old with achondroplasia. CL/F and other PK parameters of recifercept to assess exposures in different age group.

Objectives	Estimands	Endpoints

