1.1. Study Objectives, Endpoints, and Estimands

Objectives	Estimands	Endpoints
Primary:	Primary:	Primary:

 Evaluate the long-term safety and tolerability of recifercept doses and dosing regimes in participants aged ≥ 15 m to < 12 years with achondroplasia. 	N/A.	Long-term Safety and tolerability of recifercept as assessed through frequency and severity of AEs/SAEs.

 To assess long-term efficacy of recifercept to increase height growth in children with achondroplasia. 	
 The primary efficacy estimand is intended to provide a population level estimate of the effect of the IP on a continuous endpoint. 
Population-level summary: ratio between participants in the trial and a reference population [Merker et al, 2018]¹ in growth of height at 24 month; ratio between treated and reference population is observed change-from-baseline of treated participants standardized by reference participant given age and gender.
	
 Increase in height growth above expected in reference population [Merker et al, 2018].¹
Secondary:	Secondary:	Secondary:

 To evaluate the PK of recifercept in children aged ≥ 15m to ≤ 12 years old with achondroplasia. 		Population PK characterization in children aged ≥ 15 m to < 12 years old with achondroplasia. CL/F and other PK parameters of recifercept to assess exposures in different age group.

Objectives	Estimands	Endpoints

 To assess efficacy of recifercept to improve achondroplasia-related complications. 		
 Sitting height/standing height ratio. Arm span to height/length difference. Knee height:lower segment ratio. Occipito-frontal circumference. Ratio of occipito-frontal distance to occipito-mid-face measurements. z-score of the above proportionality and skull morphology where achondroplasia reference datasets exist (occipito-frontal circumference, arm span, sitting height). Fixed flexion angles at elbow. Polysomnography parameters in those with pre-existing sleep-disordered breathing at the time of enrollment. BMI. Waist:chest circumference ratio.

 Assess change in individual safety parameters. 		
 Change from baseline in safety labs, vital signs, physical examination. Rate of ADAs.

CCI [REDACTED]
	
[REDACTED]
	
[REDACTED]

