1.1.1. Primary Estimand(s)

The primary estimand is defined according to the primary objective and is in alignment with the primary endpoint. It includes the following 4 attributes:

- Population: Patients with achondroplasia, as defined by inclusion/exclusion criteria;
- Variable: Height Growth at 24 months;
- Height Growth = (Observed Change from Baseline (from study C4181005) in standing height (cm))/(Expected Change from Baseline (cm)[Merker et al, 2018]¹)

- Intercurrent event(s): Withdrawal and all events leading to missing data will be excluded from efficacy analysis and will not have their data imputed;
- Population-level summary: Mean Height growth at 24 months adjusted for age and gender.

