4.1. Hypotheses and Decision Rules

There are no statistical hypotheses for this protocol.

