4.2.1. Analyses for Longitudinal Continuous Endpoints

Mixed-effect, repeated measures (MMRM) models will be used. The fixed effects of treatment, visit, treatment-by-visit interaction, age and gender will be included. Visit will be modeled as a categorical covariate. (If the model does not converge then Visit will be modeled as a continuous covariate.) Unstructured covariance matrix will be assumed for the model errors. Compound symmetry covariance matrix will be used if the model with unstructured variance covariance doesn't converge.

When modeling the change from baseline values, the variable for visit will start with the first post-baseline visit. At each visit, estimates of least square mean (LSM) values and the LSM differences between treatment groups will be derived from the model. The corresponding p-values and 95% confidence intervals will also be derived from the model.

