5. ANALYSES AND SUMMARIES

5.1. Primary Endpoint(s)

5.1.1. Increase in height growth above expected in reference population

5.1.1.1. Main Analysis

- Estimand strategy: Hypothetical ([Section 1.1.1](#)).
- Analysis set: FAS ([Section 3](#)).
- Analysis methodology: Change from baseline relative to Merker (2018) will be analyzed using MMRM including data from Months 3-24 with gender (and possibly age), and whether a subject has switched doses of recifercept as covariates, subject (and/or time) as a random effect and an unstructured covariance matrix ([Section 4.2.1](#)).
- Intercurrent events and missing data: Data after study drug discontinuation and rescue will be excluded; intermediate missing values will not be imputed.
- The sample size, mean, standard deviation, median, minimum, and maximum at the baseline and postbaseline visits for observed standing height and change from baseline will be presented for each treatment arm.
- The least-squares (LS) means, the 95% confidence interval for the LS means, the difference between the LS means for each pair of treatment groups, and the corresponding 95% confidence interval will be presented for change from baseline in standing height for all postbaseline visits.

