Appendix 2.2. Endpoint Derivations

Height Growth

The primary efficacy endpoint is H defined by the following:

$$H_{ijkl} = \frac{Y_{ijkl} - Y_{i0kl}}{Z_{jl} - Z_{0l}},$$

where Y_{ijkl} is the observed standing height for the i th subject, at month j on dose k with gender factor l ($j=0$ denotes baseline measurement) and Z_{jl} is the mean expected standing height based on Merker for subject i 's age.

Mean expected standing height from Merker is sorted by 6 months up to age 4, while means expected values for children > 4 years are sorted per annum. Linear interpolation will be employed to calculate mean expected values so that mean standing height are sorted at 6 month intervals for children > 4 years. SAS code for the linear interpolation calculation will be provided in Appendix 4.

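### The primary estimand is one Month 24 growth ratio against the reference, but no specified model output estimates it

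*SAP*

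**What the plan says.** **The estimand.** The protocol's objectives table says: "The primary efficacy estimand is intended to provide a population level estimate of the effect of the IP on a continuous endpoint". SAP 1.1 describes the summary as a "ratio between participants in the trial and a reference population", and SAP 1.1.1 gives it as "Population-level summary: Mean Height growth at 24 months adjusted for age and gender". SAP 1.1.1 lists four attributes, and none of them names a dose. SAP Appendix 2.2 fixes the variable: "The primary efficacy endpoint is H defined by the following", followed by observed change in standing height divided by expected change in the reference cohort.

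**The outputs.** SAP 4.2.1 includes treatment, visit, their interaction, age and gender, and adds: "At each visit, estimates of least square mean (LSM) values and the LSM differences between treatment groups will be derived from the model". The methodology bullet of SAP 5.1.1.1 models change relative to the reference. Its results bullet then lists LS means with intervals, says that "the difference between the LS means for each pair of treatment groups, and the corresponding 95% confidence interval will be presented", and states that these "will be presented for change from baseline in standing height for all postbaseline visits". In the Appendix 4 code the response is named height, the fixed effects are dose, month, gender and age with no interaction, and the LS-means statement names dose only. Protocol 9.3.2 plans an ANOVA of height change at 24 months with dose terms.

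**Pooled presentation and benchmark.** SAP 4.2 presents data by dose, block and overall, and protocol 9.3.1 by dose and total. SAP 4.1 says: "There are no statistical hypotheses for this protocol". The protocol (synopsis and 9.3.2) defines growth above expected as reference growth plus 50%. The SAP does not carry that definition over.

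**The concern.** The efficacy objective asks whether treated children grow more than the reference predicts, and the estimand answers with one number for the trial's participants. The outputs requested from the model answer a different question, namely how the doses compare with each other. A reader of the report would find three dose rows and three dose-pair differences, possibly on the height scale. No adjusted estimate of the named quantity, with its uncertainty, would appear. The reader would have to choose a dose row after seeing all three, and would lose the precision of the roughly 63 children whom the estimand describes.

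**Working it through.** The visible documents give no power, alpha or derived precision to reproduce, so the check sets estimand against output and then sizes the consequence.

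**1. Estimand against outputs**

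| Feature | Estimand (SAP 1.1.1, App. 2.2) | SAP 5.1.1.1 results bullet | App. 4 code | Protocol 9.3.2 |
|---|---|---|---|---|
| Variable | H | standing-height change | height | height change |
| Contrast | participants vs reference | dose means, dose pairs | dose means | dose means |
| Time | Month 24 | every visit | averaged over visits | Month 24 |
| Age and gender | adjusted | gender, possibly age | adjusted | not in model |

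No column after the first matches the estimand on every row.

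**2. What the code returns.** Height is measured every 3 months, so Months 3 to 24 give 8 visits. Without a dose-by-month term, LS means for dose average the month levels equally. The mean month is (3 + 6 + ... + 24)/8 = 108/8 = 13.5. The code therefore gives no Month 24 value, even by dose. SAP 4.2.1 does call for the interaction and for by-visit means, so the code and the text disagree.

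**3. What dose-pair differences show.** If mean H is 1.1 on all three doses, every pairwise difference is 0. If mean H is 1.0 on all three, every difference is again 0. The differences carry no information on growth against the reference.

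**4. Precision.** Assumptions: 63 children split equally (21 per dose) and an SD of H of 0.3. The documents give neither the split nor the SD. Half-width = t × SD/√n.
- All participants: 2.00 × 0.3/√63 = 0.08.
- One dose: 2.09 × 0.3/√21 = 0.14.
- With SD 0.2 the pair is 0.05 and 0.09. With SD 0.4 it is 0.10 and 0.18.

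**5. Choosing among three doses at Month 24.** If the true mean equals the benchmark on every dose and the dose estimates are independent, the chance that at least one lower 95% limit exceeds the benchmark is 1 − 0.975³ = 0.073. For one estimate it is 0.025. The figure does not depend on the SD or the split.

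**6. Both directions, read against 1** (normal approximation, SD 0.3; SE = 0.3/√63 = 0.0378 pooled and 0.3/√21 = 0.0655 per dose).
- Uniform gain of 0.1: pooled Φ(0.1/0.0378 − 1.96) = 75%; a given dose Φ(0.1/0.0655 − 1.96) = 33%.
- Gain of 0.2 on one dose only (pooled gain 0.2/3 = 0.067): pooled Φ(0.067/0.0378 − 1.96) = 42%; that dose Φ(0.2/0.0655 − 1.96) = 86%.

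**7. Weights matter.** With illustrative dose means of 1.0, 1.1 and 1.5, equal weighting gives 1.20. Weighting by size gives (10×1.0 + 20×1.1 + 33×1.5)/63 = 1.29 for a 10/20/33 split, and (5×1.0 + 13×1.1 + 45×1.5)/63 = 1.38 for a 5/13/45 split.

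**The case against.** Several points stand against a stronger case.

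- A reader might infer that the pooled result appears nowhere. The documents do not support that: SAP 4.2 and protocol 9.3.1 allow an overall or total summary. That summary is descriptive (mean, median, SD, range), unadjusted and without an interval. The descriptive bullet in SAP 5.1.1.1 covers standing height by arm. So it does not supply the estimand, but it is not nothing.
- A reader might infer that success could be claimed from any dose at any visit. Month 24 is fixed as the time point in SAP 1.1.1, in protocol 9.3.2 and, for height, in SAP Appendix 1. Reporting earlier visits does not make them interchangeable with it. The open choice is among doses.
- A reader might take 7.3% as a breached error rate. The study is estimation only, with no hypotheses and no decision rule, so nothing is breached and no adjusted limits are called for.
- The pooled reading is partly inference. Silence about dose in SAP 1.1.1 could mean one mean per dose, and the protocol's ANOVA is by dose. SAP 4.2.1 does not say that LS means are by dose only. The description of trial participants against the reference favours pooling without settling it. This is why restating the estimand by dose is an acceptable repair.
- Pooling can hide a single effective dose, as step 6 shows. That argues for keeping the by-dose rows. It does not argue for omitting the estimand.

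**Conclusion.** The point holds in this form: the plan names one age- and gender-adjusted Month 24 mean of H, and no model output it specifies estimates that mean with a confidence interval. The mismatch rests on the text alone and needs no assumption. It is compounded by the height label in SAP 5.1.1.1 and by code that omits the required interaction and averages over visits.

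The size is illustrative. With an equal split, a dose row is √3 = 1.73 times less precise than the all-participant mean on SEs alone, or about 0.14 against 0.08 at the assumed SD of 0.3. Free choice among three dose rows raises the chance of a misleading reading from 2.5% to 7.3% when the true mean sits at the benchmark. If the benchmark is 1.5, as the protocol's plus-50% definition implies, that figure applies only when true H is near 1.5.

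**What to change.** In SAP 5.1.1.1, Appendix 1 and Appendix 4:

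1. Make H the dependent variable and label the results as H.
2. Include dose-by-month in the code and in the Appendix 1 terms, as SAP 4.2.1 already states.
3. Add one estimate: the Month 24 mean of H over all FAS participants, with a two-sided 95% interval. State the dose weights (for example, observed share), how a child who changed dose is counted, and the margins used for the other covariates.
4. Read it against 1, and also against 1.5 if the protocol's plus-50% definition stands.
5. Report the three by-dose Month 24 means of H with intervals beside it. Label pairwise differences and earlier visits as descriptive.

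If the sponsor intends a by-dose estimand, restate SAP 1.1.1 and the matching protocol text by dose instead. Items 1, 2 and 5 still apply.

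The cost is wording, a corrected model statement and an estimate statement, with no new data. The one drawback is dilution of the pooled mean if only one dose works, which the by-dose rows cover.

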5.1.1.2. Sensitivity/Supplementary Analyses

The main analysis will be repeated by using the per-protocol analysis set (PPAS) as defined in [Section 5.1.1.1](#). It will use the same methodology and summary as the main analysis.

5.2. Secondary Endpoint(s)

5.2.1. Arm span to height/length difference

5.2.1.1. Main Analysis

- Estimand strategy: Hypothetical ([Section 1.1.1](#)).
- Analysis set: FAS ([Section 3](#)).

- Analysis methodology: Change from baseline for Arm span to height/length difference will be analyzed MMRM including data from Months 3-24 with gender and whether a subject has switched doses of recifercept as covariates, subject (and/or time) as a random effect and an unstructured covariance matrix ([Section 4.2.1](#)).
- Intercurrent events and missing data: Data after study drug discontinuation and rescue will be excluded; intermediate missing values will not be imputed.
- The sample size, mean, standard deviation, median, minimum, and maximum at the baseline and postbaseline visits for observed standing height and change from baseline will be presented for each treatment arm.

The least-squares (LS) means, the 95% confidence interval for the LS means, the difference between the LS means for each pair of treatment groups, and the corresponding 95% confidence interval will be presented for change from baseline in standing height for all postbaseline visits.

5.2.1.2. Sensitivity/Supplementary Analysis

The main analysis will be repeated by using the per-protocol analysis set (PPAS) as defined in [Section 5.2.1.1](#).

5.2.2. Sitting height/standing height ratio

- Analysis set: FAS ([Section 3](#)).
- Intercurrent events and missing data: Data after study drug discontinuation and rescue will be excluded; intermediate missing values will not be imputed.
- The sample size, mean, standard deviation, median, minimum, and maximum at the baseline and postbaseline visits for observed sitting height/standing height ratio and change from baseline will be presented for each treatment arm.

5.2.3. Knee height:lower segment ratio

The analysis set, analysis methodology and intercurrent events and missing data are the same as [Section 5.2.2](#).

5.2.4. Occipito-frontal circumference

The analysis set, analysis methodology and intercurrent events and missing data are the same as [Section 5.2.2](#).

5.2.5. Ratio of occipito-frontal distance to occipito-mid-face measurements

The analysis set, analysis methodology and intercurrent events and missing data are the same as [Section 5.2.2](#).

5.2.6. Z-score of the above proportionality and skull morphology where achondroplasia reference datasets exist (occipito-frontal circumference, arm span, sitting height)

The analysis set, analysis methodology and intercurrent events and missing data are the same as [Section 5.2.2](#).

5.2.7. Fixed flexion angles at elbow

The analysis set, analysis methodology and intercurrent events and missing data are the same as [Section 5.2.2](#).

5.2.8. Polysomnography parameters in those with pre-existing sleep-disordered breathing at the time of enrolment

The analysis set, analysis methodology and intercurrent events and missing data are the same as [Section 5.2.2](#).

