## **6.8. Concomitant Therapy**

### **6.8.1. Prohibited During the Study**

Participants may not receive any medication or procedure that may affect the growth of the long bones. This includes human growth hormone (or related medicines such as IGF-1) and surgical/interventional procedures such as limb lengthening.

Participants cannot undergo surgical procedures of the bone during the course of the trial. This includes limb lengthening, guided growth (eg, 8 plates), tibial osteotomies, spinal surgery, neurosurgical procedures, or ENT bone procedures.

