### **6.8.4. Rescue Medicine**

There is no rescue therapy to reverse the AEs observed with recifercept, standard medical supportive care must be provided to manage the AEs.

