### 8.1.2. Polysomnography/Sleep Study

In participants with a documented current diagnosis of sleep disordered breathing prior to enrollment, baseline sleep study data will be collected. Baseline PSG data can be within 6 months prior to enrollment (this can be at site or a home study). The following data will be collected where available:

- Clinical summary of findings (including reported diagnosis);
- Whether study was performed in room air/oxygen/on continuous positive airway pressure;
- Apnea-hypopnea index (obstructive and total);
- Desaturation index (number of desaturations per hour >3% from baseline);
- Percentage time spent <90% oxygen saturation (SaO2);
- Percentage time spent with end-tidal carbon dioxide >50 mmHg;
- SaO2 nadir.

The sleep study will be repeated at 12 months and at the end of the study.

CCI [REDACTED]  
[REDACTED]

- [REDACTED]
- [REDACTED]
- [REDACTED]
- [REDACTED]
- [REDACTED]
- [REDACTED]
- [REDACTED]
- [REDACTED]

- CCI [REDACTED]

- [REDACTED]

- [REDACTED]

- [REDACTED]

- [REDACTED]

[REDACTED]

[REDACTED]

[REDACTED]

[REDACTED]

[REDACTED]

[REDACTED]

CCI

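### SAP 5.2.8 pools sleep-study change from baseline across room air, oxygen and CPAP recordings, so a change in respiratory support can look like a change in disease

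*SAP*

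**What the plan says.** Polysomnography parameters are a secondary efficacy endpoint (Protocol 3; SAP 2.2), restricted to children with a documented current diagnosis of sleep-disordered breathing. The baseline study may date from up to 6 months before enrollment, and "The sleep study will be repeated at 12 months and at the end of the study".

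Protocol 8.1.2 lists the data to be collected where available. Beside the apnea-hypopnea index, desaturation index, time below 90% saturation, time with raised end-tidal carbon dioxide and saturation nadir, it lists the recording condition: "Whether study was performed in room air/oxygen/on continuous positive airway pressure".

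For the analysis, SAP 5.2.8 says only "The analysis set, analysis methodology and intercurrent events and missing data are the same as" Section 5.2.2. That section covers the sitting-to-standing height ratio in the FAS. It gives descriptive statistics in which the "ratio and change from baseline will be presented for each treatment arm", with one exclusion rule: "Data after study drug discontinuation and rescue will be excluded; intermediate missing values will not be imputed".

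**The concern.** The 5.2.2 rule may serve for a body proportion, which does not depend on what the child is connected to when measured. A sleep study does. CPAP and oxygen act directly on the listed breathing and saturation parameters, so subtracting a room-air baseline from a repeat on CPAP mixes the effect of the support with any effect of recifercept.

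The error can run in either direction. A child who deteriorates, starts support and is re-studied on it can enter the table as improved. A child studied on support at baseline and off it later can enter as worse. The endpoint is confined to children with diagnosed sleep-disordered breathing, in whom support may well start or stop over 24 months. All participants receive recifercept, so no untreated arm would show the artefact.

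At stake is the by-dose description of one achondroplasia complication that the study sets out to assess.

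**Working it through.** The plan states no sample size, effect or precision for this endpoint, and SAP 4.1 sets no hypotheses, so there is no figure to reproduce. The check has three steps.

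**Step 1: follow one child through the plan.** Take a room-air baseline, CPAP started afterwards, and a Month 12 study done on CPAP.

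- *Is the treatment prohibited?* Protocol 6.8.1 bars treatments that may affect long-bone growth, and bone surgery, including "spinal surgery, neurosurgical procedures, or ENT bone procedures". CPAP, oxygen and non-bone airway procedures are not named. Protocol 6.8.3 expressly permits only topical corticosteroids for injection site reactions. The accurate description is therefore not prohibited.
- *Does it end study drug?* Starting respiratory support is not among the reasons listed in Protocol 7.1.
- *Does the rescue clause remove the study?* The SAP does not define rescue. Protocol 6.8.4 uses the word only for adverse events of the drug: "There is no rescue therapy to reverse the AEs observed with recifercept". Neither text says whether new respiratory support counts.
- *Does another SAP rule separate it?* SAP 1.1.2 gives a secondary estimand for arm span only. SAP 2.4 does not mention polysomnography in its baseline rules. SAP 5.4 plans no subset analyses. SAP 5.5.4 summarises non-drug treatments without linking them to the sleep studies. Appendix 1 covers height and arm span only.

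Unless someone reads rescue to include CPAP, Month 12 minus baseline goes into the arm mean.

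**Step 2: illustrate the size.** All inputs here are assumptions, except the enrolment of about 63 and the three doses. No true drug effect is assumed.

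(a) One child goes from 15/h on room air to 3/h on CPAP, a change of 3 - 15 = -12/h. Shift in mean change = -12/n.

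| Evaluable children n | Shift (events/h) |
|---|---|
| 20 | -12/20 = -0.6 |
| 10 | -12/10 = -1.2 |
| 7 | -12/7 = -1.7 |
| 3 | -12/3 = -4.0 |

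(b) Suppose 10%, 20% or 40% of the 63 have sleep-disordered breathing, split equally over three doses. Children per dose are 63 × 0.1/3 = 2.1, 63 × 0.2/3 = 4.2 and 63 × 0.4/3 = 8.4. One child with a fall of 10/h then moves the dose mean by 10/2.1 = 4.8, 10/4.2 = 2.4 or 10/8.4 = 1.2 events/h.

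(c) If a share c of the subset starts support and is re-studied on it, with a fall of d, the mean change is -c × d.

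| d (events/h) | c = 10% | c = 20% | c = 30% |
|---|---|---|---|
| 5 | -0.5 | -1.0 | -1.5 |
| 10 | -1.0 | -2.0 | -3.0 |
| 15 | -1.5 | -3.0 | -4.5 |

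Every sign reverses for a baseline on support and a repeat off it.

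**Step 3: test the obvious remedy.** Take three children in a dose group: two unchanged on room air, and the child from (a). Pooled mean: (0 + 0 - 12)/3 = -4.0. Same-condition mean: (0 + 0)/2 = 0. If the third child would have worsened by u on room air, which is not observed, the room-air mean for all three would be +u/3. The same-condition table removes the artefact but also drops the child who deteriorated. It cannot stand alone.

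**The case against.** The strongest reply is that this turns silence into an error. No passage says that repeat studies are done on newly started support; the protocol says only that the condition is recorded. SAP 4.2 provides for listing as well as summarising data, so the recorded condition may well be reported. A child who deteriorates may also be visible elsewhere. Exacerbation of a pre-existing condition meets the adverse event definition in Protocol 10.3.1, subject to the exception for expected disease progression, and SAP 5.5.4 summarises non-drug treatments. The summary is descriptive, with no model, interval or test. The magnitudes are assumed. Pairing by condition would not supply the missing control group.

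Most of this stands, and it limits the point. The artefact is conditional, the affected children may be traceable, and no inference fails. None of it supplies a rule, however. A listing lets a reader find the child afterwards, but the arm mean is still pooled. Without a stated rule, the decision on which studies to set aside would be made after the data are seen, in a very small subset.

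A reader might go further and infer that the rescue exclusion is empty, so that every start of CPAP is counted. The documents do not settle that. Protocol 6.8.4 concerns adverse events of recifercept, and the SAP term is undefined, so it may or may not cover respiratory support.

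**Conclusion.** The point holds as a gap in the analysis rule. As written, SAP 5.2.8 pools change from baseline across recording conditions for parameters that respond directly to those conditions, and it leaves unused an item that the protocol collects for each study. The by-dose summary can then point the wrong way for individual children and, in small groups, for the mean. On the assumed inputs, one child shifts a dose-group mean by roughly 1 to 5 events/h. That range rests on an assumed fall of 10 to 12 events/h and about 2 to 8 children per dose, neither of which is in the documents.

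A reader might infer that the plan counts starting CPAP as a benefit of recifercept, or that it systematically favours the drug. The documents do not support either reading. The artefact needs a re-study under changed support, it can run in both directions, and its frequency is unknown. Nor is there a false-positive risk in the testing sense, because nothing is tested. The consequence is a potentially misleading descriptive table for a secondary endpoint. It should be corrected before analysis.

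**What to change.** Replace the cross-reference in SAP 5.2.8 with a rule of its own.

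- Present change from baseline by paired recording condition: same condition, changed condition, and condition not recorded. Do not pool across them.
- Report by dose the number of children who newly start or stop CPAP or oxygen, or have an airway procedure, between studies. Flag studies done after such a procedure.
- State whether rescue covers these events, or delete the term for this endpoint.
- State that the same-condition table selects on a post-baseline event, because children who worsen and start support leave it, and that it must be read with the counts of new starters and the changed-condition rows.

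The cost is SAP wording and a few small tables. No visit, procedure or new data item is needed, and no clinical rule is proposed. The price is fewer pairs in the same-condition table, which may be nearly empty for some doses. The not-recorded row is needed because Protocol 8.1.2 collects these items only where available.
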